6. TYPE OF TRIAL AND DESIGN

6.1. Phase of the clinical trial

It is considered a low level intervention phase clinical trial to evaluate the effectiveness and safety of a sanitary product marketed for a different use than the accredited one.

6.2. Design and comparator

Experimental, randomized and controlled study with the usual technique of inserting a venipuncture catheter until now. Incomplete clinical trial, blind to third parties, in healthy volunteers, which consists of three arms, in which they are intervened and the comparator is applied.

Three interventions are established and a common comparator for all of them. Interventions:

1. Application of dry topical heat.
2. Application of high stagnation pressure.

3. Application of dry topical heat and high stagnation pressure. That is, the combination of the previous two.

Comparator:

1. Usual clinical practice, until now

Therefore, all individuals will be subjected to one of the three interventions and the comparator, whose sequence corresponds to the two periods established by the clinical trial of bioequivalence.

Therefore, all individuals will be subjected to one of the three interventions and the comparator, whose sequence corresponds to the two periods established by the clinical trial of bioequivalence.

It is understood that it is a crossover clinical trial because each subject is exposed to an intervention, and it is their own control; it is exposed to the comparator, whose purpose is to reduce the intraindividual variability and accentuate the effectiveness of the intervention per se. It is an incomplete crossing because it is not possible to subject each individual to the three interventions and it must be only one per random assignment. This impossibility could be supported by the low frequency of clinical trials of four periods carried out in the accessible environment.

In this way, any of the interventions assigned to it can be compared with the current procedure for antebrachial venous cannulation

6.3. Random assignment of interventions.

The intervention and the sequence of application of the intervention with the comparator will be randomly assigned.

They will be assigned with sealed envelopes where inside the corresponding intervention to be applied, the comparator and the corresponding sequence will be detailed. Emerging the following options:

1. CA-> C. Topical first period heat. Comparator in the second period.
2. C-> CA. Comparator in the first period. Topical heat in the second period.
3. P-> C. High pressure in the first period. Comparator in the second period.
4. C-> P. Comparator in the first period. High pressure in the second period.

5. CA + P -> C. Combination of dry topical heat and high stagnation pressure in the first period. Comparator in the second period.

6. C-> PA + C. Comparator in the first period. Combination of dry topical heat and high stagnation pressure in the second period.

As a result of these options and the coverage of the Clinical Trials Unit of the University Hospital of La Princesa is twelve individuals in each group, the following sealed envelopes for each group are established

- Four contain topical heat and comparator intervention

- Two will be topical first period heat. Comparator in the second -> [CA-> C]
- Two will be comparator in the first period. Topical heat in the second -> [C-> CA]

- Four intervention of high pressure and comparator

- Two will be high pressure in the first period. Comparator in the second -> [P-> C]
- Two will be comparator in the first period. High pressure in the second -> [C-> P]

- Four combined (topical heat and high pressure) and the comparator

- Two will be combination in the first period. Comparator in the second -> [CA + P-> C]
- Two will be comparator in the first period. Combination in the second -> [C-> CA + P]

This scheme of twelve envelopes will be carried out five times to address a sufficient sample size, of sixty subjects, to assume the estimated losses and, finally, to obtain the number of subjects, who have completed both periods, calculated to obtain a statistical significance of the results.

Due to the inclusion / exclusion criteria established, and which will result from the first evaluation VIA (36), an equivalent number of individuals in each arm will be sought.

In each envelope, the chronological order of application of the intervention-comparator will be included, by default and without previous knowledge.

It will be randomized only once, in the first period. In the second period, the remaining sequence will be applied. Figure 1

[figure not shown]

Figure 1. Design flow diagram. Own elaboration.

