6.4. Masking

The present study is considered blind to third parties; simple blinding due to logistics problems is not considered. Both the principal investigator and the nurses and subjects participating in the study know the method that will be applied to them. However, if it is considered blind to third parties, since the assessment of hemolysis is carried out by team personnel who are unaware of the method used in antebraichial venous cannulation for each sample analyzed.

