9.4. Development of fieldwork of the trial

The first evaluation of the VIA scale (36) will be carried out, according to the number of optimal puncture points (PPO), before the application of the arm assigned by the main researcher and will correspond to the inclusion and exclusion criteria; pre-intervention assessment. This will be transcribed as the first VIA scale assessment (36).

In the interventions, the VIA scale will be evaluated twice (36). The second assessment will be carried out after the application of the intervention or randomly assigned comparator; and before performing venipuncture.

In the case of the comparator, it will only be evaluated once; It will not be assessed if it denotes a change of stage, since no intervention is applied. If this corresponds to the first period, the registration stage of the inclusion / exclusion criteria will be transcribed, if it corresponds to the second period, the corresponding nurse will assess it.

In both cases, the intervention or comparator will be applied, the success or failure in successful venipuncture will be recorded on the first attempt. In the case of failure, the attempt number to which the catheterization was possible will be recorded. Table 2

| ORGANIZATION CHART ACCORDING TO VISITS | | |
|---|-----------------|---|
| ENROLLMENT VISIT | FIRST DAY ENTRY | SECOND DAY ENTRY |
| 
 1. Information Sheet 2. Informed consent form. 3. Training for the nurses listed on the form. | X | 
 1. Subjects inclusión according to inclusión and exclusión criteria VIA assessment 2. Randomized assignment 3. Intervention/comparator assigned application. 4. Post intervention VIA assessment. 5. VAS pain assessment. 6. FITZPATRICK scale skin assessment 7. Hemolysis analysis. |

Table 2. Organization chart according to visits. Own elaboration.

This organization chart, Table 2, will be specific to the first period of the clinical trial. Another detailed organization chart has been prepared for the two study periods in section 9.7.3.

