13. PRACTICAL CONSIDERATIONS

13.1. Training of the nursing team and collaborators / observers

It is considered necessary to train the nursing team with certain scales that, except for the VAS / Numeric scale, are not commonly used in routine clinical practice. Likewise, interventions require specific knowledge a priori.

No training is contemplated, because the nurses are familiar with the material resources they will use, only a training is planned with the possibility of asking questions and these will be solved and / or clarified. The main researcher will belong to the collaborating nursing team and will support them in the fieldwork.

Similar situation is that of collaborators / observers of the intensity of hemolysis. Those involved in the evaluation of blood samples will be trained, although they are trained in the use of the material involved.

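### Known sets of 12 envelopes in an open trial make late allocations partly predictable, and the plan does not require a group's eligibility to be final before its first envelope is opened

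*Combined protocol and SAP*

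**What the plan says.** - **Set content (6.3).** The unit takes twelve subjects per admission group, and on that basis "the following sealed envelopes for each group are established". Each set holds four heat, four high-pressure and four combined assignments, and each method is split evenly between the two orders. For heat, for example: "Four contain topical heat and comparator intervention", of which "Two will be topical first period heat. Comparator in the second" and the other two run in the reverse order.
- **Repeats (6.3).** "This scheme of twelve envelopes will be carried out five times to address a sufficient sample size, of sixty subjects". Subjects are randomised once, in the first period.
- **Concealment (6.3).** The envelopes are sealed and the order is meant to be unknown beforehand. Opaque or numbered envelopes, a custodian, and the handling of an envelope left over when a subject proves ineligible are not described.
- **Masking (6.4).** "Both the principal investigator and the nurses and subjects participating in the study know the method that will be applied to them". Only the haemolysis assessors are blind.
- **Eligibility and assignment (9.4).** The first VIA rating, based on the number of optimal puncture points, takes place "before the application of the arm assigned by the main researcher and will correspond to the inclusion and exclusion criteria". Table 2 puts this rating first and randomised assignment second, both on the second day of entry. Sections 7.2 and 7.3 make VIA stage and recent fluid intake eligibility criteria.
- **Staff (13.1).** "The main researcher will belong to the collaborating nursing team and will support them in the fieldwork".

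**The concern.** Sealing an envelope hides its content only if that content cannot be worked out from the envelopes already opened. Here the composition of every set is written in the protocol, and each opened assignment becomes visible to the staff. If eligibility is still being decided for later subjects, the person making a VIA call may already have a fair idea of the next method. VIA is a bedside rating, so a borderline call has some room in it.

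What is at stake is the main objective (sections 2.11 and 5.2.1): identifying the best of the three methods. Each subject receives only one of them, so the ranking compares different people, about 20 per method at most. If eligibility calls leaned on the expected method, vein quality could differ between the three groups. Section 4.2 reports that the benefit depends on venous perception. VIA stage is not in the variable list of section 14.1.1 from which the logistic regression in 14.1.3.1.2 takes its explanatory variables, so the analysis as written would not adjust for such a difference.

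**Working it through.** **Inputs, all from section 6.3.** Set of 12; 4 envelopes per method; 2 per sequence; 6 with the intervention first and 6 with the comparator first; 5 sets.

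**The plan's own figure.** 5 × 12 = 60 subjects, which agrees with section 14.1.2; 5 × 4 = 20 per method and 5 × 2 = 10 per sequence.

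**Assumptions, not stated in the plan.** Envelopes are in random order within a set, subjects are assessed and assigned one at a time, and an observer tallies each draw and always guesses the method with most envelopes left.

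**Formula.** With r envelopes left, P(correct guess) = E(largest number left of any one method) / r, averaged over all possible draws so far.

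**By hand for the last three draws:**
- *Draw 10 (three left).* There are C(12,3) = 220 equally likely remainders. All one method: 3 × C(4,3) = 12. All different: 4 × 4 × 4 = 64. Two and one: 220 − 12 − 64 = 144. P(correct) = (12 × 1 + 144 × 2/3 + 64 × 1/3) / 220 = 0.588.
- *Draw 11 (two left).* C(12,2) = 66. Both the same method: 3 × C(4,2) = 18, so the method is certain in 18/66 = 27.3% of sets. P(correct) = 0.273 + 0.727 × 0.5 = 0.636.
- *Draw 12.* Always known: 1.000.

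**All draws, by exact enumeration:**

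| Draw | 1 | 2 | 3 | 4 | 5 | 6 | 7 | 8 | 9 | 10 | 11 | 12 |
|---|---|---|---|---|---|---|---|---|---|---|---|---|
| P(correct method), % | 33.3 | 36.4 | 40.0 | 41.2 | 42.7 | 45.9 | 47.6 | 49.7 | 55.2 | 58.8 | 63.6 | 100 |

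**Averages:**
- Full set: 6.144 / 12 = 51.2%, against 4 / 12 = 33.3% by chance. Over five full sets this is 30.7 correct of 60, against 20.
- Last three draws: (58.8 + 63.6 + 100) / 3 = 74.1%.
- Only 9 drawn: 392.0 / 9 = 43.6%. Only 10 drawn: 450.8 / 10 = 45.1%.
- Order (intervention or comparator first), full set: 7.716 / 12 = 64.3%, against 50%.
- Full sequence, full set: 4.328 / 12 = 36.1%, against 16.7%.

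**If the group's eligibility is final first.** The envelopes can still be guessed, but no eligibility decision in that group remains open for a guess to influence.

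**The case against.** **Eligibility may already be batched.** A reader might infer from Table 2 that each subject's eligibility is judged immediately before that subject's own draw. The documents do not say so. Table 2 gives the order of steps in a day, which fits rating all twelve subjects first equally well. Subjects enter the night before (9.2) and the room seats twelve (9.1). If the group is rated first, the risk largely disappears. This stands: what can be shown is that the order across subjects is unspecified.

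**The figures are upper values.** They need someone who tallies every draw and a set that is used up. VIA stage and fluid intake exclude subjects on the day, and the plan does not say whether unused envelopes carry over. Section 6.3 says only that similar numbers per arm will be sought after the first VIA evaluation, without a mechanism. This also stands. With 9 or 10 draws the near-certain end of the set is not reached, although 44-45% is still above 33%.

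**Each subject is their own control.** A reader might infer that the McNemar comparison is biased. It is largely protected, because a shift in vein quality affects a subject's intervention and comparator attempts alike. The protection does not fully extend to ranking the methods: by section 4.2 the gain itself may vary with venous perception, and section 10.2.1 judges effectiveness on raw success rates.

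**No bias has been measured.** A reader might attach a size by assuming how many subjects are borderline and how much worse they do. The documents give neither figure, and even the sign is open. Stage I is excluded (7.2) because of a preceding study which found more benefit with compromised venous perception (4.2). That suggests stage I is the good-vein group, but the wording about low stages is ambiguous. Sampling error also matters: assuming 85% success and 18-20 subjects per method, the standard error of a between-method difference is √(2 × 0.85 × 0.15 / n), or 11-12 percentage points.

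**Conclusion.** The point holds as a gap in allocation concealment, not as a demonstrated bias. The set content is fixed and published, methods are open, and no rule closes a group's eligibility before its envelopes start to be opened. The guessing rates of 51% overall, 74% for the last three draws and 100% for the twelfth hold only with one-at-a-time assessment, a fully used set and an observer who keeps count; with 9 or 10 draws the average is 44-45%.

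The exposed comparison is the between-subject ranking of the three methods. The documents do not show that eligibility calls would in fact be influenced, and they do not allow the size or direction of any effect to be computed. The change is worth making because it costs little and because selection of this kind would be hard to detect or repair afterwards. It ranks as a cheap improvement.

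**What to change.** In sections 6.3 and 9.4, require that the VIA rating and fluid-intake eligibility of every subject in an admission group be completed and signed before that group's first envelope is opened. Table 2 should show the same order for the group as a whole.

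The cost is protocol wording, with no extra subjects or staff. The small downside is that all of the group's VIA ratings must precede the first cannulation. The sets of 12 can stay as they are, which keeps the balance of methods within each full group.

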9.2. Workflow of Clinical Trials Unit for bioequivalence studies

In any of the bioequivalence trials, subjects are recruited who meet the inclusion and exclusion criteria added to those described above.

It supposes an income around 24 h, according to the design of each trial, and the intravenous cannulation to each subject to perform the pharmacokinetics of each drug. A recruiting visit is made to inform about the clinical trial in question, the Patient Information Sheet and the Informed Consent are delivered.

It is ensured that they do not carry any disease; the following is done:

- Blood and urine extraction. Biochemistry, Hematology, Serology and urinary sedimentation. - Vital signs. Blood Pressure (BP), Heart Rate (HR), Temperature (T).
- Anthropometry Weight, Size, Body Mass Index (BMI)
- Electrocardiogram (ECG).
- Physical exam. Concomitant treatment.

In this visit will be carried out, only the selection of subjects according to the criteria of inclusion / exclusion of the trial that takes place in the unit. Subjects enter the night before the prescribed day to perform pharmacokinetics. Next day, at 08:00 h, intravenous cannulation is started by the nursing team. The subjects remain fasting from dinner on the day of admission. The medication is always administered after the canalization and once a basal blood sample has been extracted in tubes whose additive is dipotassium ethylenediaminetetraacetic acid (K₂EDTA).

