14. STATISTICAL ANALYSIS PLAN

14.1. Main analysis

14.1. 1. Definition of variables

Primary variable

Successful venipuncture at the first attempt. Dichotomous qualitative variable. Success / Failure

Secondary variables

Successful venipuncture frequency. Discrete quantitative variable. (1,2,3,4)

Visual intensity of hemolysis. Discrete quantitative variable. It is measured in stadiums.

Scale of expressed pain intensity (VAS). Discrete quantitative variable.

Scale skin types Fitzpatrick. Discrete quantitative variable.

Ingestion of liquids (less than 500 ml) in the last 6-8h prior to cannulation. Discrete quantitative variable (measured in glasses); it will be transcribed continuously for statistical analysis.

Affiliation of individuals

Respected fasting of 6-8 hours. Dichotomous qualitative variable.

Age. Quantitative variable continues.

Sex. Dichotomous qualitative variable.

Race. Discrete quantitative variable. 1 -> Caucasian 2 -> Black 3 -> Asian 4 -> Latin

BP. Continuous quantitative variable.

HR. Continuous quantitative variable.

T. Continuous quantitative variable.

BMI Continuous quantitative variable.

14.1. 2. Sample size calculation

The sample calculation is performed with the GRANMO calculator (63). It assumes a random risk (alpha) of 5% and a statistical power (beta) of 80%; for which it is tried to prove the veracity of the null hypothesis, of bilateral type.

That is, the risk of rejecting the null hypothesis when this is true is 5%, and the probability of not rejecting it being false is 20%.

In the literature, the success of peripheral intravenous canals was recorded in the first attempt, using the usual technique, in 74% of the cases (55). Currently, a proportion of peripheral intravenous cannulation has been registered at the first attempt of 73%, in an ultrasound ecoguided manner (33). In relation to the second successful attempt, in the usual clinical practice it amounts to 92% of the cases and, in the ultrasound ecoguided to 91% (33.55).

For the present work we intend to achieve a 95% success rate in antebrachial venous cannulation at the first attempt. Thus, overcome with one of the alternative methods proposed in this study the cumulative proportion of the second attempt of the usual and eco guided clinical practice.

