It is considered a clinically relevant difference the successful venous cannulation at the first attempt when, not only allows the cannulation at the first attempt of those cases that hypothetically would be observed, but accumulate to those cases that, in a way observed in the literature, the cannulation has been achieved at the second attempt, and hypothetically, that success can be achieved in the first attempt.

The comparative indicators are based on the comparison method and the reduction of intraindividual variability. It is considered a root of the experience, one of them is lost; An average of both percentages has been made, thus obtaining a 12% loss approximately.

Therefore, the calculation of the sample size should be followed through the modality of proportions, paired measures (repeated in a group). Fix in the proportion with pre-intervention event 0.74, in the proportion with post-intervention event 0.95, and the loss ratio 0.12.

Finally, the estimated sample size is 60 subjects.

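### Five groups of 12 envelopes give 60 randomised only if nobody fails the VIA or fluid check, and section 6.3 gives no rule for unused envelopes or for how equal arms are to be reached

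*Combined protocol and SAP*

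**What the plan says.** Section 6.3 provides a set of 12 envelopes for each group of 12 admitted volunteers: four per intervention arm, two per sequence. It then says "This scheme of twelve envelopes will be carried out five times to address a sufficient sample size, of sixty subjects", and explains that 60 is meant to absorb the estimated losses. Section 14.1.2 gives the same total: "Finally, the estimated sample size is 60 subjects".

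On the timing of eligibility:

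- Section 9.2 says the recruiting visit makes "only the selection of subjects according to the criteria of inclusion / exclusion of the trial that takes place in the unit". Volunteers are admitted the evening before cannulation.
- Section 9.4 places the first VIA rating "before the application of the arm assigned by the main researcher and will correspond to the inclusion and exclusion criteria". Table 2 puts eligibility with VIA first and randomised assignment second, both on the second day of entry.
- Sections 7.2 and 7.3 exclude VIA stage I and fluid intake above 500 ml in the 6-8 hours before cannulation.

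On balance, section 6.3 says that, because of the eligibility criteria and the first VIA rating, "an equivalent number of individuals in each arm will be sought". It gives no procedure for this. The same section says that intervention and sequence are assigned at random from sealed envelopes, without prior knowledge of the content.

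**The concern.** The scheme is exactly 5 x 12, with no spare places. A volunteer found ineligible on the morning of cannulation leaves a chair empty and an envelope unused. The protocol does not say whether that volunteer is replaced, whether the envelope passes to the next group, or whether a sixth group would get a new set or the leftovers.

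The balance sentence raises a second question. It links equal arms to the VIA result, which is known immediately before allocation. The trial is open (section 6.4), the principal investigator works in the nursing team (section 13.1), and the make-up of each set is fixed and known. No serial numbering or opening order is stated, and nothing requires every VIA rating in a group to be finished before the first envelope is opened. The last allocations in a group can then be deduced, so a borderline VIA rating could follow the expected arm.

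What is at stake is the choice of the best intervention, which is the main objective in section 5.2.1. That comparison is between different subjects, about 60 / 3 = 20 per arm.

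**Working it through.** **The plan's own figure.** Section 14.1.2 states: "It assumes a random risk (alpha) of 5% and a statistical power (beta) of 80" per cent, two-sided, and "Fix in the proportion with pre-intervention event 0.74, in the proportion with post-intervention event 0.95, and the loss ratio 0.12". No discordant proportion is given. Assuming independence, it is 0.74 x 0.05 + 0.26 x 0.95 = 0.284, and the difference is 0.21. The simple McNemar formula gives (1.960 + 0.842)² x 0.284 / 0.21² = 50.55, so 51 pairs, and 51 / 0.88 = 57.95, so 58. The formula with separate null and alternative variances and a discordant proportion of 0.31 gives 52.75 / 0.88 = 59.95. The stated 60 is therefore reproduced closely enough, as a number of randomised subjects inflated for later loss.

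**What the 12% covers.** Section 14.1.2 describes it as an average of two percentages. Section 7.4 lists as lost data failed catheterisation in the first period and non-attendance at the second. Neither is a VIA or fluid exclusion, so the 60 contains no allowance for screen failures.

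**Five groups with exclusions.** The exclusion rate e is my assumption, shown over a range, and admissions are taken to stop at five groups with no replacement. The formulas are:

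- mean randomised = 60(1 - e)
- completers = 0.88 x 60(1 - e)
- chance that all 60 are eligible = (1 - e)^60
- admissions needed on average for 60 randomised = 60 / (1 - e)
- power of the pooled McNemar test = Φ[(0.21√n - 1.960√0.284) / √(0.284 - 0.21²)], with n the completers

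| e | Mean randomised | Completers | Chance of 60 | Pooled power | Admissions needed (groups of 12) |
|---|---|---|---|---|---|
| 0 | 60 | 52.8 | 100% | 83.7% | 60 (5) |
| 5% | 57 | 50.2 | 4.6% | 81.7% | 64 (6) |
| 10% | 54 | 47.5 | 0.2% | 79.5% | 67 (6) |
| 20% | 48 | 42.2 | below 0.01% | 74.3% | 75 (7) |
| 30% | 42 | 37.0 | below 0.01% | 68.3% | 86 (8) |

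**Chance imbalance if unused envelopes are dropped.** In 10,000 simulated trials, the number eligible per group was binomial (12, 1 - e) and envelopes were drawn in random order from each set. The mean gap between largest and smallest arm was 1.5, 2.2 and 3.0 subjects at e = 5, 10 and 20%. A gap of 4, say 16 v 20 instead of 18 v 18, changes the variance factor of a between-arm contrast from 1/18 + 1/18 = 0.1111 to 1/16 + 1/20 = 0.1125, or about 1%. Random non-use of envelopes adds no bias. The concern about the arms is therefore concealment, not unequal numbers.

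**The case against.** Four points can be made for the plan.

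First, a reader might infer that the trial must fall short of 60. The documents do not support that. Eligibility precedes randomisation in Table 2, so an excluded volunteer need not use an envelope. Section 9.1 allows groups of 12 until all recruits are covered, and section 14.2.3.2 contemplates running the protocol in more than one bioequivalence trial to reach the required number. This stands, and the shortfall is conditional. But section 6.3 still states five runs, and no envelope rule exists for a further group.

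Second, a reader might infer that the balance sentence tells staff to choose envelopes. It does not. It reads as an aim, section 6.3 says allocation is random and sealed, and balance can be pursued without selection by carrying envelopes forward. This also stands. What remains is an aim tied to the VIA result with no random mechanism behind it.

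Third, it is unclear whether the main researcher named in section 9.4 assigns the arm or carries out the VIA rating. Either way, that person knows the methods applied and works in the nursing team.

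Fourth, sections 2.13 and 9.9 use 54, which is also the mean number randomised at 10% exclusion. That does not settle the matter: 60 x 0.88 = 52.8, not 54, and the documents do not say whether 54 counts enrolled, randomised or completing subjects. The two totals need reconciling.

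**Conclusion.** The point holds in a limited form. As written, five groups of 12 give 60 randomised only if nobody fails the VIA or fluid check, and the 12% allowance does not help. If admissions stop at five groups, 57, 54 or 48 are randomised on average at an assumed 5, 10 or 20% exclusion. The true rate is not in the documents, so the size of any shortfall is unknown. The pooled within-subject McNemar test is little affected at low exclusion: 81.7% power at 5% and 79.5% at 10%, assuming a discordant proportion of 0.284.

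The weightier part is allocation. Seeking equal arms in light of VIA, in an open trial with known sets and no stated opening order, leaves the between-arm comparison open to selection. This is a risk that the text leaves open. The documents do not show that non-random allocation is planned. The change should be made, because it is nearly free and answers both parts.

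**What to change.** In section 6.3, replace the set of 12 per group with one pre-generated, serially numbered stack of 60 sealed envelopes in permuted blocks across the six sequences. Then:

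- Rate and record VIA and fluid eligibility for every subject in the group, in a fixed order such as chair number, before the first envelope is opened.
- Give each eligible subject the next number in that order.
- Carry unused envelopes forward to later groups. A part-used block could make the next allocations predictable, so keep the block structure from those who rate VIA.
- Delete the sentence "an equivalent number of individuals in each arm will be sought".
- Either state that groups continue until 60 are randomised or, if groups are capped at five, restate the expected number as 60 x (1 - exclusion rate), with the assumed rate given.

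The cost is re-numbering the envelopes, a wording change, and rating the whole group before the first allocation. There is also either a possible further group (six in all at 5 or 10% exclusion, seven at 20%) or a smaller stated number.
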